2.4.2 Supportive secondary endpoints

2.4.2.1 Efficacy endpoints

Insulin dose after 26 weeks of treatment

The actual daily insulin dose after 26 weeks of treatment will be analysed using an ANCOVA model including treatment and previous antidiabetic treatment as fixed factors and baseline HbA_{1c} value and insulin dose at screening as covariates.

Responder for HbA_{1c} after 26 weeks of treatment

Two dichotomous endpoints (responder/non-responder) will be defined based on whether a subject has met a specific target level after 26 weeks of treatment:

- ADA HbA_{1c} target (HbA_{1c} < 7.0%)
- International Diabetes Federation (IDF) HbA_{1c} target (HbA_{1c} ≤ 6.5%)

Analysis of each of the two responder endpoints will be based on a logistic regression model with treatment and previous antidiabetic treatment as fixed factors and baseline HbA_{1c} value as a covariate.

HbA_{1c} responder endpoints without weight gain

Responder for HbA_{1c} without weight gain after 26 weeks of treatment will be defined as HbA_{1c} < 7.0% or ≤ 6.5% at end of treatment and change from baseline in body weight below or equal to zero. Analysis of each of the two responder endpoints will be based on a logistic regression model with treatment and previous antidiabetic treatment as fixed factors and baseline HbA_{1c} and body weight values as covariates.

HbA_{1c} responder endpoints without hypoglycaemic episodes

Responder for HbA_{1c} without hypoglycaemic episodes after 26 weeks of treatment will be defined as HbA_{1c} < 7.0% or ≤ 6.5% at end of treatment and without severe or BG confirmed episodes during the last 12 weeks of treatment. Analysis of each of the two responder endpoints will be based on a logistic regression model with treatment and previous antidiabetic treatment as fixed factors and baseline HbA_{1c} values as a covariate.

HbA_{1c} responder endpoints without hypoglycaemic episodes and weight gain

Responder for HbA_{1c} without hypoglycaemic episodes and weight gain after 26 weeks of treatment will be defined as HbA_{1c} < 7.0% or ≤ 6.5% at end of treatment, without severe or BG confirmed episodes during the last 12 weeks of treatment, and change from baseline in body weight below or equal to zero. Analysis of each of the two responder endpoints will be based on a logistic regression model with treatment and previous antidiabetic treatment as fixed factors and baseline HbA_{1c} and body weight values as covariates.

Fasting plasma glucose (FPG)

Change from baseline in FPG after 26 weeks of treatment will be analysed using the standard ANCOVA model.

Waist circumference

Change from baseline in waist circumference after 26 weeks of treatment will be analysed using the standard ANCOVA model.

Beta-cell function (fasting insulin, fasting C-peptide, fasting glucagon, and HOMA-β)

In addition to fasting insulin, fasting C-peptide, and fasting glucagon, one derived parameter will be calculated; Beta-cell function (HOMA-β). The calculation of the HOMA endpoint will be done as follows:

- Beta-cell function (%) = $20 \cdot \text{fasting insulin}[\mu\text{U/mL}] / (\text{FPG}[\text{mmol/L}] - 3.5)$

These endpoints after 26 weeks of treatment will be analysed separately using the standard ANCOVA model. In these statistical analyses the endpoint will be log-transformed and so will the baseline covariate.

Fasting lipid profile

Cholesterol, low density lipoprotein cholesterol (LDL cholesterol), high density lipoprotein cholesterol (HDL cholesterol), very low density lipoprotein cholesterol (VLDL cholesterol), triglycerides, and free fatty acids after 26 weeks of treatment will be analysed separately using the standard ANCOVA model. In these statistical analyses the endpoint will be log-transformed and so will the baseline covariate.

Self-measured plasma glucose (SMPG) 9-point profile

Three endpoints from the 9 point SMPG profile will be defined:

- 9-point profile
- Mean of the 9-point profile, defined as the area under the profile (calculated using the trapezoidal method) divided by the measurement time
- Post-prandial PG increments (from before meal to 90 min after for breakfast, lunch and dinner). The mean increment over all meals will be derived as the mean of all available meal increments

A linear mixed effect model will be fitted to the 9-point SMPG profile data. The model will include treatment, previous antidiabetic treatment, time, the interaction between treatment and time and the interaction between previous antidiabetic treatment and time as fixed factors and subject as random effect, where measurements within subjects will be assumed correlated with a compound symmetry covariance matrix. From the model mean profile by treatment and relevant treatment differences will be estimated and explored.

Change from baseline after 26 weeks of treatment in mean of the 9-point profile and post-prandial increment endpoints will be analysed separately using the standard ANCOVA model.

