trtpn	LSMeans frequency, IDeg	-2.3055	-1.3799	0.1584	0.09971	0.2516

Least Squares Means Estimate

Effect	Label	Estimate	Standard Error	z Value	Pr > z	Alpha
trtpn	Treatment odds ratio, IDegLira / IDeg	1.8007	0.2638	6.82	<.0001	0.05

Least Squares Means Estimate

Effect	Label	Lower	Upper	Exponentiated
trtpn	Treatment odds ratio, IDegLira / IDeg	1.2836	2.3179	6.0541

Least Squares Means Estimate

Effect	Label	Exponentiated Lower	Exponentiated Upper
trtpn	Treatment odds ratio, IDegLira / IDeg	3.6096	10.1540

9: Responder for HbA1c treatment target without weight gain – supportive statistical analysis – full analysis set

Parameter Code=HB65WOWG

The GENMOD Procedure

Model Information

Data Set	WORK.ADATA2	
Distribution	Binomial	
Link Function	Logit	
Dependent Variable	AVALC	Analysis Value (C)

Number of Observations Read	453
Number of Observations Used	453
Number of Events	62
Number of Trials	453

Class Level Information

Class	Levels	Values
trtpn	2	1 2
PREAD	2	BASAL INSULIN + METFORMIN BASAL INSULIN + METFORMIN + ONE OTHER OAD

Response Profile

Ordered Value	AVALC	Total Frequency
1	Y	62
2	N	391

PROC GENMOD is modeling the probability that AVALC='Y'.

Parameter Information

Parameter	Effect	trtpn	PREAD
Prm1	Intercept		
Prm2	trtpn	1	
Prm3	trtpn	2	
Prm4	PREAD		BASAL INSULIN + METFORMIN
Prm5	PREAD		BASAL INSULIN + METFORMIN + ONE OTHER OAD
Prm6	HbA1cCBL		
Prm7	WGtbl		

Criteria For Assessing Goodness Of Fit

Criterion	DF	Value	Value/DF
Log Likelihood		-159.3887	
Full Log Likelihood		-159.3887	
AIC (smaller is better)		328.7775	
AICC (smaller is better)		328.9117	
BIC (smaller is better)		349.3569	

Algorithm converged.

Responder for HbA1c treatment target without weight gain - supportive statistical analysis - full analysis set

Parameter Code=HB65WOWG

The GENMOD Procedure

Analysis Of Maximum Likelihood Parameter Estimates

Parameter	DF	Estimate	Standard Error	Wald 95% Confidence Limits	
Intercept	1	-1.3809	1.5664	-4.4511	1.6892
trtpn 1	1	2.4694	0.6029	1.2877	3.6512
trtpn 2	0	0.0000	0.0000	0.0000	0.0000
PREAD BASAL INSULIN + METFORMIN	1	0.0531	0.2874	-0.5103	0.6165
PREAD BASAL INSULIN + METFORMIN + ONE OTHER OAD	0	0.0000	0.0000	0.0000	0.0000
HBA1CBL	1	-0.3826	0.1438	-0.6645	-0.1007
WGTL	1	0.0107	0.0108	-0.0104	0.0318
Scale	0	1.0000	0.0000	1.0000	1.0000

Analysis Of Maximum Likelihood Parameter Estimates

Parameter	Wald Chi-Square	Pr > ChiSq
Intercept	0.78	0.3780
trtpn 1	16.77	<.0001
trtpn 2		
PREAD BASAL INSULIN + METFORMIN	0.03	0.8535

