PREAD BASAL INSULIN + METFORMIN + ONE OTHER OAD		
HBA1CBL	7.08	0.0078
WGTL	0.99	0.3188
Scale		

NOTE: The scale parameter was held fixed.

Least Squares Means Estimates

Effect	Label	Estimate	Standard Error	z Value	Pr > z	Alpha
trtpn	LSMeans frequency, IDegLira	-1.4921	0.1553	-9.61	<.0001	0.05
trtpn	LSMeans frequency, IDeg	-3.9615	0.5867	-6.75	<.0001	0.05

Least Squares Means Estimates

Effect	Label	Lower	Upper	Exponentiated	Exponentiated Lower	Exponentiated Upper
trtpn	LSMeans frequency, IDegLira	-1.7965	-1.1877	0.2249	0.1659	0.3049
trtpn	LSMeans frequency, IDeg	-5.1113	-2.8117	0.01903	0.006028	0.06010

Least Squares Means Estimate

Effect	Label	Estimate	Standard Error	z Value	Pr > z	Alpha
trtpn	Treatment odds ratio, IDegLira / IDeg	2.4694	0.6029	4.10	<.0001	0.05

Least Squares Means Estimate

Effect	Label	Lower	Upper	Exponentiated
trtpn	Treatment odds ratio, IDegLira / IDeg	1.2877	3.6512	11.8157

Responder for HbA1c treatment target without weight gain - supportive statistical analysis - full analysis set

Parameter Code=HB65WOWG

The GENMOD Procedure

Least Squares Means Estimate

Effect	Label	Exponentiated Lower	Exponentiated Upper
trtpn	Treatment odds ratio, IDegLira / IDeg	3.6243	38.5206

Responder for HbA1c treatment target without weight gain - supportive statistical analysis - full analysis set

Parameter Code=HBA7WOWG

The GENMOD Procedure

Model Information

Data Set	WORK.ADATA2	
Distribution	Binomial	
Link Function	Logit	
Dependent Variable	AVALC	Analysis Value (C)

Number of Observations Read	453
Number of Observations Used	453
Number of Events	105
Number of Trials	453

Class Level Information

Class	Levels	Values
trtpn	2	1 2
PREAD	2	BASAL INSULIN + METFORMIN BASAL INSULIN + METFORMIN + ONE OTHER OAD

Response Profile

Ordered Value	AVALC	Total Frequency
1	Y	105
2	N	348

PROC GENMOD is modeling the probability that AVALC='Y'.

Parameter Information

Parameter	Effect	trtpn	PREAD
Prm1	Intercept		
Prm2	trtpn	1	
Prm3	trtpn	2	
Prm4	PREAD		BASAL INSULIN + METFORMIN
Prm5	PREAD		BASAL INSULIN + METFORMIN + ONE OTHER OAD
Prm6	HBALCBL		
Prm7	WGTLBL		

Criteria For Assessing Goodness Of Fit

Criterion	DF	Value	Value/DF
Log Likelihood		-211.2368	
Full Log Likelihood		-211.2368	
AIC (smaller is better)		432.4737	
AICC (smaller is better)		432.6079	
BIC (smaller is better)		453.0531	

Algorithm converged.

Responder for HbA1c treatment target without weight gain - supportive statistical analysis - full analysis set

Parameter Code=HBA7WOWG

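### The two strictest HbA1c responder composites have about 3 IDeg responders, and the SAP's ordinary logistic regression mildly inflates their odds ratios; a Firth-penalised fit would be better at little cost

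*SAP*

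**What the plan says.** The responder endpoints stand under "2.4.2 Supportive secondary endpoints", so they lie outside the confirmatory hierarchy of SAP 2.4.1. There are four families, each at HbA1c below 7.0% and at 6.5% or below: HbA1c alone, without weight gain, without hypoglycaemia, and without either. The model sentence is the same for each: "Analysis of each of the two responder endpoints will be based on a logistic regression model". The families that include weight have treatment and previous antidiabetic treatment as "fixed factors and baseline HbA_{1c} and body weight values as covariates". Protocol 17.4.2.1 plans the same models. Neither document names a penalised or exact method, or says what to report if an arm has few responders or none.

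The statistical documentation bound with the SAP shows what was run. Outputs 7 to 10 are ordinary binomial-logit fits, headed "Analysis Of Maximum Likelihood Parameter Estimates", with Wald limits. For HbA1c of 6.5% or below without weight gain, output 9 gives "Number of Events 62" (of 453 subjects). The IDeg least-squares mean on the logit scale is "trtpn LSMeans frequency, IDeg -3.9615 0.5867 -6.75". The odds ratio is in "trtpn Treatment odds ratio, IDegLira / IDeg 1.2877 3.6512 11.8157", with its 95% limits in "trtpn Treatment odds ratio, IDegLira / IDeg 3.6243 38.5206". Responder counts by arm are not shown.

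**The concern.** Maximum-likelihood log odds ratios are biased away from zero when one arm has very few events, and they are infinite when it has none. Rarity in the IDeg arm could be foreseen from the design. Protocol 5.2 and 5.6 cap IDeg at 50 units so that the arms separate. Protocol 6.2 steers baseline HbA1c to a median of 8.5%. SAP 2.1 puts only 150 subjects on IDeg. The strictest composites then add further conditions to the lower HbA1c target.

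The two composites affected carry the largest of the eight reported odds ratios, 11.82 and 11.58; the other six run from 6.05 to 10.37. The bias has one direction, in favour of IDegLira. Had no IDeg subject responded, the planned analysis would have given no usable estimate, and the SAP offers no substitute.

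**Working it through.** **1. The stated odds ratio reproduces.** In output 9 the log odds ratio is 2.4694 with SE 0.6029. exp(2.4694) = 11.82, and exp(2.4694 ± 1.96 × 0.6029) gives 3.62 to 38.52, as printed.

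**2. Arm sizes.** These come from output 2, as residual variance divided by the squared SE of the least-squares mean. IDegLira: 0.7569 / 0.05007² = 301.9, so 302. IDeg: 0.7569 / 0.07082² = 150.9, so 151.

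**3. IDeg responders (inferred).** Two routes for output 9:
- From the mean: odds exp(−3.9615) = 0.01903, p = 0.01903/1.01903 = 0.0187, and 151 × 0.0187 = 2.8.
- From the SE: 1/0.5867² = 2.905 = np(1−p), so np = 2.96.

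The crude table confirms the count. With 62 responders in all:

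| IDeg responders | Crude OR | SE of log OR |
|---|---|---|
| 2 | 18.5 | 0.726 |
| 3 | 11.98 | 0.601 |
| 4 | 8.7 | 0.527 |
| Output 9 (adjusted) | 11.82 | 0.603 |

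Only 3 fits. For the version with the hypoglycaemia clause (output 10, 61 responders), 3 IDeg responders give a crude OR of 11.73 with SE 0.601; the output has 11.58 and 0.603. The same method gives about 7, 7, 9, 10, 21 and 21 IDeg responders for the other six endpoints.

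**4. Expected bias.** Take true rates of 59/302 and 3/151 and calculate the exact binomial expectation of the crude log odds ratio. Maximum likelihood, given at least one IDeg responder: bias +0.086, and exp(0.086) = 1.09. Firth, over all outcomes: −0.001. A simulation of the adjusted model gave a mean of +0.10 and a median of +0.05 for maximum likelihood where finite, and about 0 for Firth. That simulation assumes a baseline HbA1c SD of 1.18, a weight SD of 12.5 kg and an even split of previous treatment, none of which the documents give.

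**5. Chance of no IDeg responder.** (1 − 3/151)^151 = 4.8%. At a 2% rate, 0.98^151 = 4.7%. At an assumed 1% rate, 0.99^151 = 22%; the documents give no planning rate.

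**6. Firth on the crude tables.** For a 2×2 table the Firth odds ratio adds 0.5 to each cell.
- 59/302 v 3/151: (59.5/243.5)/(3.5/148.5) = 10.37, against 11.98.
- 58/302 v 3/151: (58.5/244.5)/(3.5/148.5) = 10.15, against 11.73.
- 98/302 v 7/151 (below 7.0% without weight gain): 9.3, against 9.9.

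For the first table 10.37/11.98 = 0.866, which is 13% lower. The log gap of 0.144 is 0.24 of the SE of 0.601. In simulated adjusted fits with exactly 3 IDeg responders the gap was 0.156, which would take 11.82 to about 10.1 and 11.58 to about 9.9.

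**7. Intervals for 59/302 v 3/151.** Wald 3.7 to 38.9; profile likelihood 4.3 to 49.7; Firth profile 4.0 to 38.1. At the rates in step 4, nominal 95% Wald intervals cover in 96.6% of samples with a finite estimate. Fisher's exact p is about 2 × 10⁻⁸.

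**The case against.** The strongest objection is that nothing went wrong. Both fits converged with finite estimates and limits, so a reader who infers that these odds ratios could not be estimated is contradicted by the output; an infinite estimate was only a prospective risk. The chance of about 5% uses a rate learned from the results, and the 22% figure rests on a rate found nowhere in the documents. All of this stands.

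It is also tempting to read the whole 13% gap between the two estimators as bias. It is not. The gap compares two estimates on one data set, while the bias is an average over repeated samples and is about 9%. One cannot say that the true odds ratio is 10.4 rather than 12.0. A reader might further infer that all eight responder odds ratios are inflated to a degree that matters. Only two have about 3 IDeg responders, and the next sparsest move little (9.9 to 9.3).

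The endpoints are supportive, the Wald interval covers adequately when it exists, and a span of 3.6 to 38.5 already shows the imprecision. Finally, replacing the planned estimator after seeing a sparse cell would itself be data-driven. That is a good reason to label a Firth result supplementary now. It does not remove the planning gap: the SAP has no provision for sparse cells in composites whose rarity could be expected.

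**Conclusion.** The point holds as a low-cost improvement of low severity. Two of eight supportive odds ratios come from about 3 of 151 IDeg responders. At that rate ordinary maximum likelihood overstates the odds ratio by about 9% on the log-scale average, in favour of IDegLira, with a chance of about 5% of no finite estimate. Firth estimation removes nearly all of this bias and stays finite. Direction and significance are unchanged, and no confirmatory test or type I error is involved.

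The conclusion rests on three things: the IDeg count of 3, which is inferred from the output and not stated; the observed rates taken as the truth for the bias calculation; and, for the adjusted figures only, the assumed covariate distributions. The crude calculation needs no covariate assumptions and gives nearly the same estimator gap (0.144 against 0.156 log units).

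**What to change.** In SAP 2.4.2.1, for the composites with HbA1c of 6.5% or below and no weight gain (or for any responder endpoint with few responders in an arm), specify Firth-penalised logistic regression with the same factors and covariates. Give profile penalised-likelihood 95% confidence intervals, and report responder counts by arm. If the rule is worded by count, fix the threshold in the text. Since outputs exist, show the Firth result beside the planned fit for the two composites, labelled supplementary.

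The cost is one model option in the program and a line or two in the SAP. The odds ratios become slightly less favourable. Model-based response frequencies are also pulled slightly towards one half: in the crude table the IDeg rate becomes 3.5/152 = 2.3% instead of 3/151 = 2.0%. Observed proportions should therefore be shown too.

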### **Self measured plasma glucose (SMPG) 9-point profile**

Three endpoints from the 9 point SMPG profile will be defined:

- 9-point profile
- Mean of the 9-point profile, defined as the area under the profile (calculated using the trapezoidal method) divided by the measurement time
- Post-prandial PG increments (from before meal to 90 min after for breakfast, lunch and dinner). The mean increment over all meals will be derived as the mean of all available meal increments

A mixed effect model will be fitted to the 9-point profile data. The model will include treatment, time, interaction between treatment and time, and previous anti-diabetic treatment as fixed factors and the baseline value as a covariate. An unstructured residual covariance matrix within the same subject is employed. From the model mean profile by treatment and relevant treatment differences will be estimated and explored.

Change from baseline after 26 weeks of treatment in mean of the 9-point profile and post-prandial increment endpoints will be analysed separately using the standard ANCOVA model.

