#### 3.2 Titration

Dose will be adjusted twice weekly by the subject on two days 3-4 days apart. The investigator will support titration at all contacts.

Titration should be performed based on the mean of three pre-breakfast SMPG values measured two days before and on day of titration. Titration should preferably be performed on the same days of the week throughout the trial. The dose adjustment will be performed according to [Table 1](#).

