### 2.1.16 Statistical considerations

**Rationale:** To be compliant with the updates made in other sections of the protocol the statistical considerations have been updated accordingly. Main update is related to hypoglycaemia definitions.

**Impact:** Section 17 updated.

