1.2 Scope of the statistical analysis plan

This Statistical Analysis Plan (SAP) is based on final Protocol version 5.0 (06-Dec-2016).

The scope of this SAP is to add one sensitivity analysis for change from baseline in HbA_{1c} after 26 weeks of treatment and several sensitivity analyses for confirmatory secondary endpoints, and performed other minor changes. For further details on the changes see section [3](#).

2 Statistical considerations

Novo Nordisk will analyse and report data from all sites together.

All analyses of efficacy and safety endpoints will be based on the full analysis set (FAS). The analysis of the primary endpoint and the confirmatory secondary endpoint, change from baseline in body weight after 26 weeks of treatment, will be repeated on the per-protocol (PP) analysis set and the completer analysis set (CAS) for sensitivity purposes. All efficacy endpoints will be summarised using the FAS and safety endpoints will be summarised using the safety analysis set (SAS).

The impact of protocol deviations and outliers may be investigated further in sensitivity analyses if deemed relevant.

Unless otherwise specified, all continuous measurements will be summarised descriptively at each visit by treatment using observed data. After 26 weeks of treatment, descriptive statistics will be presented based both on observed and last observation carried forward (LOCF) imputed data. Endpoints that are analysed untransformed and endpoints that are not formally analysed are summarised by the arithmetic mean, standard deviation (SD), median, and minimum and maximum value. Endpoints that are analysed log-transformed are summarised by the geometric mean and coefficient of variation (CV).

For measurements over time, mean values will be plotted to explore the trajectory over time. LOCF imputed data will be used as the basis for plotting data, if not otherwise specified. For endpoints that are analysed log-transformed, the geometric mean values will be plotted.

A standard analysis of covariance (ANCOVA) model will be applied for the continuous primary and secondary endpoints. The model includes treatment and previous antidiabetic treatment (basal insulin and metformin or basal insulin, metformin and other OAD(s)) as fixed factors and the corresponding baseline value as a covariate. In the following, this model will be referred to as the standard ANCOVA model.

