A listing of subjects with at least one post baseline value \geq 20 ng/l will be done. The listing will include age, gender, calcitonin measurements over time and AE history (including preferred term, onset and stop dates).

Urinalysis

Categorical urinalysis parameters will be summarised descriptively by:

- Shift from baseline to EOT (using the number of subjects in the different categories)
- Subjects with at least one post baseline measurement outside reference range will be listed

Insulin and GLP-1 antibodies

Insulin antibodies (IDeg specific, cross-reacting to human insulin and total) will be summarised with arithmetic mean, standard deviation (SD), median, and minimum and maximum value by treatment and treatment week, and their mean over time will be plotted. Correlations will be explored graphically as follows. Insulin antibodies (IDeg specific, cross-reacting to human insulin and total) will be plotted against HbA_{1c} after 26 weeks, HbA_{1c} change from baseline after 26 weeks, and dose after 26 weeks. Change from baseline to FU1 in insulin antibodies (IDeg specific, cross-reacting to human insulin and total) will be plotted against HbA_{1c} after 26 weeks, HbA_{1c} change from baseline after 26 weeks, and dose after 26 weeks.

GLP-1 antibodies (liraglutide specific, cross-reacting to native GLP-1, liraglutide *in vitro* neutralising and *in vitro* neutralising to native GLP-1) will be summarised by number of subjects (N) and percentage of subjects (%) with positive and negative samples.

Antibody measurements will be listed by subject and visit together with associated age, sex, BMI, HbA_{1c} and dose

3 Changes to the statistical analyses planned in the protocol

- Additional sensitivity analysis added to use pattern mixture model to evaluate the sensitivity of using LOCF for primary endpoint HbA_{1c}
- Sensitivity analyses for confirmatory secondary endpoints have been added.
- One minor change regarding the analysis model to the supportive secondary endpoint of 9-point self-measured plasma glucose has been made

4 References

-
- ¹ U.S. Department of Health and Human Services, Food and Drug Administration. Guidance for Industry. Diabetes Mellitus: Developing Drugs and Therapeutic Biologics for Treatment and Prevention, Draft Guidance. 2008.
- ² European Medicines Agency. Committee for Proprietary Medical Products (CPMP): Points to consider on switching between superiority and non-inferiority (CPMP/EWP/482/99). EMEA 2000. 2000.

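### Minor, cheap improvement: the SAP's 9-point SMPG profile model uses compound symmetry and no baseline covariate, unlike the protocol text shown, and SAP section 3 does not say what changed or why

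*SAP*

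**What the plan says.** Protocol 17.4.2.1 (version 2.0) fits a mixed model to the 9-point profile with treatment, time, their interaction, "previous anti-diabetic treatment as fixed factors and the baseline value as a covariate". On the covariance it says: "An unstructured residual covariance matrix within the same subject is employed".

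SAP 2.4.2.1 fits treatment, previous treatment, time and the interactions of both treatment terms with time. It names subject as a random effect and adds that "measurements within subjects will be assumed correlated with a compound symmetry covariance matrix". There is no baseline term. The purpose is descriptive: "From the model mean profile by treatment and relevant treatment differences will be estimated and explored".

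SAP 1.2 announces some added sensitivity analyses "and performed other minor changes. For further details on the changes see section" 3. For this endpoint, section 3 says only: "One minor change regarding the analysis model to the supportive secondary endpoint", naming the 9-point profile. It gives neither the content of the change nor a reason.

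The SAP rests on protocol version 5.0, which is not shown in full. Amendment 1 updated section 17 and describes this as "Main update is related to hypoglycaemia definitions". The section 17 edits shown in later amendments (antibody text, confirmatory secondary endpoints, sidedness of tests, calcitonin plots) do not mention the profile model.

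**The concern.** Compound symmetry gives all nine times the same variance and every pair of times the same covariance. If c is that common covariance, the covariance between the post-meal minus pre-meal increments at two different meals is c − c − c + c = 0. So the model assumes that a subject's breakfast increment says nothing about the dinner increment.

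Equal variances were doubtful before any data existed. Appendix A, section 3.2 says: "Titration should be performed based on the mean of three pre-breakfast SMPG values". Fasting values are therefore steered towards a narrow target, and post-meal values are not.

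Two kinds of result depend on the assumption. The nine single-time treatment differences all use one pooled variance, so an interval can be too wide where the true variance is small and too narrow where it is large. The treatment-by-time test uses the compound-symmetry residual as its error term. In addition, a reader of section 3 cannot tell which parts of the model were changed on purpose.

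**Working it through.** **1. The two models.**

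| | Protocol 17.4.2.1 (v2.0) | SAP 2.4.2.1 |
|---|---|---|
| Within-subject covariance | unstructured, 9 × 10 / 2 = 45 parameters | compound symmetry, 2 parameters |
| Baseline value | covariate | absent |
| Previous treatment × time | absent | present |

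The statistical documentation (item 18, dated 22 January 2020) confirms that the SAP model was run. It reports 2 covariance parameters and 39 design columns: 1 (intercept) + 2 (treatment) + 18 (treatment by time) + 18 (previous treatment by time) = 39. No column is left for baseline.

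**2. Reproducing the printed standard errors.** The variance components are 1.9446 and 3.3601, total 5.3047, correlation 1.9446 / 5.3047 = 0.37. Arm sizes of 302 and 151 are inferred from 453 subjects at 2:1. Then √(5.3047/302) = 0.1325 and √(5.3047/151) = 0.187 (printed at time 1: 0.1325 and 0.1875). For a difference, √[5.3047 × (1/302 + 1/151)] = 0.2296 (printed at time 1: 0.2296). The printed standard errors of the nine same-time differences run only from 0.2296 to 0.2346, as one pooled variance dictates.

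**3. Treatment-by-time test.** The nine printed differences have mean −0.940, and their squared deviations sum to 1.088. Numerator: 1.0882 / 8 = 0.13603. Error: 3.3601 × 0.009934 = 0.03338. F is about 4.08, against 3.99 printed, so the compound-symmetry residual is the error term. Recomputing p for F = 3.99 on (8ε, 3517ε) degrees of freedom, with ε the Greenhouse-Geisser factor:

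| ε | 1 | 0.7 | 0.5 | 1/8 (lower bound) |
|---|---|---|---|---|
| p | 0.0001 | 0.0008 | 0.003 | 0.046 |

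This is approximate, because 90 of 4077 values are missing.

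**4. One check of fit.** Under compound symmetry the mean of three meal increments has variance 2 × 3.3601 / 3 = 2.24. The ANCOVA of that mean (item 20) has residual variance 2.9392. Taking baseline out again gives 2.9392 × (448 + 43.59) / 449 = 3.22. The single-meal residual variances, 6.6362, 7.1139 and 5.7871, sum to 19.537 and are close to the compound-symmetry value 2 × 3.3601 = 6.72. The between-meal covariance is (9 × 2.9392 − 19.537) / 6 = 1.153, a correlation of 1.153 / (19.537/3) = 0.18 instead of 0. This is one derived statistic, from slightly different data sets.

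**5. Size at single times: illustration only.** No document gives SMPG variance by time. Assume that fasting SMPG variance lies between that of laboratory FPG without baseline, 2.9791 × (449 + 13.22) / 450 = 3.06, and the pooled 5.30.

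- Fasting intervals would be 0 to 32% too wide: √(5.3047/3.06) = 1.32.
- Suppose three times have variance 3.06, the other six share one variance, and the average stays 5.3047. Those six have (47.742 − 9.18) / 6 = 6.43. The factor is √(6.43/5.3047) = 1.10, so intervals are about 9% too narrow.
- Suppose instead that pre-lunch and pre-dinner have an assumed 4.5. The remaining four times have (47.742 − 9.18 − 9) / 4 = 7.39. The factor is 1.18, so intervals are about 15% too narrow.

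**6. Baseline.** Partial R² = F / (F + df) for baseline in the ANCOVAs of the profile mean and the meal increments runs from 19.10 / (19.10 + 442) = 4.1% to 45.67 / (45.67 + 445) = 9.3%. Since the standard error scales with √(1 − R²), adjustment would save about 2 to 5% of it.

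**The case against.** The change is disclosed. Section 3 names the endpoint, 2.4.2.1 gives the new model in full, and anyone with both documents can list the differences. That stands: what is missing is the description and the reason, and nothing suggests concealment.

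A reader might infer that the SAP departs from the protocol version in force. The documents do not settle this. Section 3 confirms that the SAP model differs from the protocol's, but version 5.0 is not shown in full, so which term changed, and when, is unknown.

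A reader might also infer that the last pre-breakfast difference (time 9: −0.3993, p = 0.083) would have been significant under a better model. It would fall below 0.05 only if fasting SMPG variance were under about 4.13. The lower value of 3.06 is borrowed from a laboratory measurement, so this carries no weight. The fasting comparison also has its own baseline-adjusted FPG analysis (−0.4165, p = 0.0160).

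The evidence of misfit is thin and comes from output that should not be held against the SAP's authors. The single-meal variances agree with compound symmetry. Nor is 9% a limit on how narrow post-meal intervals may be, because it presumes equal variances at the remaining times. All of this stands and limits the claim. It does not remove the prior reason to doubt equal variances, or the low cost of relaxing them.

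**Conclusion.** The point holds as a minor improvement. The two texts differ in three respects, and section 3 explains none of them. Compound symmetry was a doubtful choice for a profile whose fasting points are steered by titration. Standard errors at single times may be wrong in either direction, by amounts the documents do not determine; the percentages above rest on assumed variances.

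The consequences are small. The treatment-by-time p remains 0.046 at the Greenhouse-Geisser lower bound. Apart from the two fasting times, the weakest differences (times 5 and 8, |t| 3.16 and 3.04) would need standard errors about 1.61 and 1.54 times as large to lose p < 0.05. The mean profile and the increments have their own baseline-adjusted ANCOVAs. The profile itself is not among the endpoints in protocol 4.2.2.2, and it lies outside the confirmatory test hierarchy. A reader might infer that the efficacy claim is weakened; it is not.

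**What to change.** In SAP 2.4.2.1, specify an unstructured within-subject covariance with no separate random subject effect. Add the baseline (Visit 2) SMPG value as covariate and state whether it is the value at the same time of day. Keep the previous-treatment-by-time term. Name one fallback covariance in case the model does not converge. Heterogeneous compound symmetry would free the variances, but with a common correlation it does little for correlation between meal increments.

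In SAP section 3, list the three differences from the protocol model (covariance, baseline, interaction) and give the reason for each.

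The cost is a few lines of text and code. No new data are needed, because protocol 8.2.13 already collects a profile in the week before Visit 2. There would be 45 covariance parameters for 453 subjects; the unstructured HbA1c and body-weight models (21 parameters, same subjects) converged. The downsides are possible non-convergence and the loss of records without a baseline value. The documents do not give that number: the mean-profile ANCOVA used 443 of 453 subjects, but the baseline-adjusted mean-increment ANCOVA used 452, so 10 is not a count of missing baselines.
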